This prospective, multicentre, randomized, controlled, two parallel group, open-label trial based on pooled design was conducted across four tertiary care centres with study protocol approved by the institutional ethics committees of all participating centres: Adichunchanagiri Institute of Medical Sciences (AIMS), B. G. Nagara, JSS Medical College and Hospital (JSS), Mysore and Mysore Medical College and Research Institute (MMC&RI), Mysore and Rajarajeswari Medical College and Hospital (RRMCH), Bangalore, all centres in the state of Karnataka, India. The study was done under the supervision of primary investigator [name] N (AIMS) with the other principal investigators included [name], [name] and [name] M, respectively. The study protocol was approved by the institutional ethics committees of all participating centres and registered with ClinicalTrials.gov (Identifier: NCT07046403; Protocol Record Id: AIMS/IEC/206/2025). The investigators adhered to the applicable regulatory requirements and the trial was conducted in accordance with Good Clinical Practice guidelines and the Declaration of Helsinki. Written informed consent was obtained from all participants and patient confidentiality was rigorously maintained.

Patient screening and eligibility

The study population consisted of patients seeking treatment for DFUs. Eligible patients were those willing to participate and comply with scheduled visits on days 7, 14, 21, 28 (intervention period) and 35 (follow-up period). The study included two phases: screening and treatment. The screening phase aimed to determine patient eligibility for the treatment phase. During the screening, a series of assessments were conducted, including demographics, medical history, concomitant medications, vital signs, physical examination, foot ulcer history, clinical infection signs at the ulcer site, and ankle-brachial index measurement.

Inclusion criteria: Patients aged 18-75 years with type 1 or type 2 diabetes mellitus presenting with chronic foot ulcers were screened for eligibility. Target ulcer size between 5.0-20.0 cm² measured post-debridement; ulcer duration of 4-20 weeks; adequate circulation documented by ankle-brachial index (ABI) 0.7-1.3; and glycated haemoglobin (HbA1c) <12%.

Exclusion criteria included: Patients were excluded from the study if they met any of the following criteria: presence of active infection requiring systemic antibiotics, confirmed

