osteomyelitis or exposed bone in the wound bed, current use of immunosuppressive therapy, diagnosis of active malignancy, pregnancy or lactation, end-stage renal disease requiring dialysis, acute Charcot foot deformity, previous amputation that would affect target ulcer offloading capacity, and participation in other investigational studies within the preceding 30 days.

Randomization and Blinding

Eligible patients were randomized 1:1 using computer-generated random sequence with variable block sizes (4, 6, 8) stratified by site. Allocation concealment was maintained using sequentially numbered opaque sealed envelopes. Due to the nature of the interventions, participants and investigators could not be blinded to treatment allocation. However, outcome assessors for wound parameters (photograph-based planimetry was performed by a central reader), histological analysis and quality of life measurements were blinded to treatment assignment.

Interventions

All participants received standardized wound care including debridement, infection control, glycaemic optimization, and pressure offloading using total contact casting or removable cast walkers. Subjects who met the study's inclusion criteria after the screening period were randomized into one of two groups:

- a. The HPTC arm (n=60) received high-purity type-I collagen-based skin substitute (Helicoll®, Encoll Corp, USA) that was carefully trimmed to precisely cover the wound bed, followed by application of standard of care (SOC) wound dressing. The reapplication schedule for HPTC was determined by the treating investigator's clinical judgment based on wound assessment and healing progress.
- b. The dHACM group (n=60) received dehydrated human amnion/chorion membrane applied according to manufacturer instructions with concurrent application of standard of care (SOC), with repeat applications performed as clinically indicated based on wound healing response.

During the four-week treatment phase, patients were re-evaluated on days 7, 14, 21, and 28. The SOC bandage in both groups included an identical three-layer dressing systems: non-adherent paraffin gauze (primary layer), absorbent gauze pads (secondary layer), and soft roll with crepe bandage (tertiary layer) - standardized 3-layer dressing system.

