If the study ulcer was found to be 100% re-epithelialized during the visit, no further study procedures were conducted at that time. The patient was then scheduled for a follow-up visit after one week to confirm the healing. If complete healing was not observed, an assessment was performed to check for signs of clinical infection. If an infection was diagnosed, treatment with topical antimicrobials (betadine, chlorhexidine) or oral antibiotics was allowed, but the use of topical antibiotics (erythromycin, polymyxin, mupirocin) was prohibited.

Following the infection assessment, the ulcer was cleaned, photographed, and debrided at the investigator's discretion to ensure a clean, granulating ulcer base with minimal adherent slough. The SOC was then reapplied, and the patient was instructed to keep the bandaging dry. The patient was also advised to contact or visit the study site if the bandage became soiled or was removed. Topical antibiotics specifically on the wound were prohibited.

Systemic antibiotics were permitted when clinically needed.

Study completion

Patients completed the study four weeks after their first treatment visit. However, if a patient's study ulcer closed before the four-week mark, they were considered to have completed the study at that time. Complete healing of the study ulcer was defined as 100% re-epithelialization with no drainage. Throughout the treatment period, patients had the right to refuse participation or withdraw from the study at any time without prejudice. If a patient chose to withdraw from the study, their last recorded wound measurement was carried forward and used to calculate the change in wound size and their final outcome.

Outcome Measures

Primary Outcome:

1. Proportion of participants achieving wound size reduction at 4 weeks, measured using digital planimetry. Wound area was monitored at visits on days 7, 14, 21, 28 (intervention period) and 35 (follow-up period)

Secondary Outcomes:

1. Histological assessment of vascular incursion and wound biology was performed using punch biopsies (2mm diameter) obtained from the wound edge on day 5 post-treatment initiation. Histological parameters were evaluated using standardized scoring scales, including:

- a. vascular infiltration assessed on a 0-3 scale based on vessel count per high-power field,
- b. neo-epithelialization measured on a 0-3 scale based on epithelial migration distance from the wound edge,

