Vascular infiltration	Assessed by counting new blood vessels (0–3 scale)	Minimal vascular ingrowth (<5 vessels/HPF)	0
		Mild infiltration (5–10 vessels/HPF)	1
		Moderate infiltration (11–20 vessels/HPF)	2
		Abundant infiltration (>20 vessels/HPF)	3
Neo-epithelialization	Measured as epithelial migration distance from wound edge (0–3 scale)	No epithelial migration	0
		Minimal migration (<25% wound coverage)	1
		Moderate migration (25–75% coverage)	2
		Extensive migration (>75% coverage)	3
Fibroblast activity	Quantified by counting α -SMA positive fibroblasts per HPF and assessment of fibroblast morphology (0–3 scale)	Sparse, inactive fibroblasts	0
		Moderate cellularity, minimal matrix production	1
		High cellularity, active-matrix synthesis	2
		Very high activity with extensive matrix deposition	3
Capillary density	Evaluated using CD31 staining, counted as vessels per mm^2 of tissue		
Inflammatory response	Graded semi-quantitatively (0–3 scale)	Minimal inflammatory infiltrate	0
		Mild chronic inflammation	1
		Moderate mixed inflammation	2
		Severe acute inflammation	3
Collagen deposition	Assessed using Masson's trichrome staining (0–3 scale)	Minimal collagen matrix	0
		Loose, immature collagen	1
		Moderate organized collagen	2
		Dense, mature collagen architecture	3

*Data presented as scoring criteria; all parameters assessed using standardized histological grading scales

Sample Size Calculation

Based on previous studies, we anticipated 85% of HPTC patients and 55% of dHACM patients would achieve wound reduction. With 80% power to detect a 25% absolute difference in complete wound closure at 5 weeks, 5% significance level, and assuming 10% dropout rate, a total of n=120 with 60 participants per group were required, pooled in from across 4 centres.

Statistical Analysis

Statistical analyses were performed using SPSS version 28.0 (IBM Corp, Armonk, NY, USA) and R version 4.3.0. Continuous variables were expressed as mean \pm standard deviation or median (interquartile range) based on normality testing using Shapiro-Wilk test. Categorical variables were presented as frequencies and percentages.

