Between-group comparisons for continuous variables used independent t-tests or Mann-Whitney U tests. Chi-square or Fisher's exact tests were employed for categorical variables. Time-to-event analysis used Kaplan-Meier curves with log-rank tests. Mixed-effects models analysed repeated measures data. All analyses followed the intention-to-treat principle, with sensitivity analyses using per-protocol populations. A two-sided p-value of less than 0.05 was considered statistically significant for all analyses, with p-values less than 0.001 indicating highly significant differences between groups.

Data collection and follow-up

Demographic data, medical history, comorbidities, and baseline wound characteristics were recorded. Laboratory parameters, including haemoglobin, albumin, and glycated haemoglobin (HbA1c), were obtained at baseline and follow-up visits.

Patients were evaluated at baseline, day 5, day 7, day 14, day 21, day 28, and day 35. At each visit, wound measurements were performed using standardized digital planimetry, with wound area calculated in cm^2 . Histopathology examination results were recorded on baseline day 0 and day 5 after application. Digital photographs were taken for documentation and independent assessment. Complete wound closure was defined as 100% epithelialization without drainage or dressing requirements. Any adverse events, if they occurred, were duly noted and notified. Scar quality and durability were assessed at each visit, with patient satisfaction assessed at the fifth week, during the one-week follow-up.

Ethical Considerations

The study was conducted in accordance with ethical principles outlined in the Declaration of Helsinki. Written informed consent was obtained from all participants before enrolment.

Participant confidentiality was maintained throughout the study period. Data safety monitoring was performed by an independent committee.

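### Free improvement: allocation is stratified by site, but no named between-group test uses site or baseline, so power is forgone if either predicts outcome

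*Combined protocol and SAP*

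**What the plan says.** Under Randomization and Blinding, patients are allocated 1:1 with "variable block sizes (4, 6, 8) stratified by site". Study Design and Setting lists four centres. Under Outcome Measures the primary outcome is "Proportion of participants achieving wound size reduction at 4 weeks, measured using digital planimetry".

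The Statistical Analysis section names one method per type of variable:

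- Proportions, which include the primary outcome: "Chi-square or Fisher's exact tests were employed for categorical variables".
- Continuous outcomes: "Between-group comparisons for continuous variables used independent t-tests or Mann-Whitney U tests".
- Time to closure: "Time-to-event analysis used Kaplan-Meier curves with log-rank tests".
- Repeated measurements: "Mixed-effects models analysed repeated measures data".

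None of these sentences mentions site, baseline ulcer area or any other covariate. No CMH test, logistic regression, ANCOVA, stratified log-rank test or Cox model appears anywhere. Sample Size Calculation describes the 120 patients as "pooled in from across 4 centres". Study Design and Setting also calls the design pooled, but neither statement specifies an analysis.

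**The concern.** Blocking within site removes chance imbalance between sites from the treatment comparison. A test that ignores site still counts between-site variation in its variance. Two separate points follow.

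1. **Site.** If success rates differ between centres, the pooled test's variance is too large, its true type I error falls below 5%, and power is given up. If they do not differ, nothing is lost by pooling.
2. **Baseline.** Eligibility spans a fourfold range of ulcer area ("Target ulcer size between 5.0-20.0" cm²), and area is not a stratification factor. Ignoring it keeps type I error near 5% but forgoes precision if area is prognostic. For histology, day-0 and day-5 biopsies are to be compared, but nothing says how the day-0 value enters the comparison between arms.

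The unlisted mixed-model terms also leave the analyst a choice that could be made after the data are seen.

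**Working it through.** **Inputs from the document.** Four sites; 1:1 allocation blocked within site; 60 per arm; two-sided 5%; 80% power; 10% dropout; 55% anticipated on dHACM; a 25-point difference to detect.

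**Reproducing the plan's sample size.** Take 55% plus 25 points, so 80% versus 55%, with mean 0.675:

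n = [1.96·√(2·0.675·0.325) + 0.8416·√(0.80·0.20 + 0.55·0.45)]² / 0.25² = (1.298 + 0.537)² / 0.0625 ≈ 53.9, so 54 per arm.

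54 / 0.9 = 60 per arm, the stated figure. This is why 55% versus 80% is used below.

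**Why pooling is conservative.** With equal sites and no treatment effect, the pooled test uses variance p̄(1−p̄). Under blocked allocation the true variance is the mean of pₛ(1−pₛ) over sites. The approximate type I error is 2·[1 − Φ(1.96·√(pooled/within))]. The site rates are assumed, with mean 55%:

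| Rates by site | Pooled | Within | Ratio | Approx. alpha |
|---|---|---|---|---|
| 55% at all four | 0.2475 | 0.2475 | 1.000 | 5.0% |
| 45, 52, 58, 65% | 0.2475 | 0.2421 | 0.978 | 4.8% |
| 35, 50, 60, 75% | 0.2475 | 0.2263 | 0.914 | 4.0% |
| 25, 45, 65, 85% | 0.2475 | 0.1975 | 0.798 | 2.8% |

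**Simulation of the primary comparison.** There were 100,000 trials per scenario, with 15 per arm per site (60 per arm) or 14, 13, 14, 13 (54 per arm). A common log-odds ratio (1.19, 1.21, 1.28, 1.43 down the rows) fixes the marginal difference at 25 points. Neither test is continuity-corrected. Each cell shows pooled chi-square / site-stratified CMH.

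| dHACM rates by site | Alpha, 60/arm | Power, 60/arm | Alpha, 54/arm | Power, 54/arm |
|---|---|---|---|---|
| 55% at all four | 5.4 / 5.4% | 84.8 / 84.4% | 4.5 / 4.6% | 80.7 / 80.6% |
| 45-65% | 5.1 / 5.2% | 85.0 / 85.0% | 4.2 / 4.8% | 80.9 / 81.2% |
| 35-75% | 4.3 / 4.8% | 85.7 / 87.0% | 3.6 / 5.1% | 81.5 / 83.0% |
| 25-85% (extreme) | 3.1 / 5.0% | 86.7 / 90.0% | 2.5 / 5.0% | 82.6 / 86.9% |

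With uneven sites (24, 12, 12, 12 per arm), power is 84.4 / 83.9% with no site effect and 83.8 / 88.3% at 25-85%. A wider assumed spread (control rates 15-91%, SD 1.5 on the log-odds scale; 6,000 trials) gives 85.0 / 92.0% at 54 per arm.

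**Time to closure.** Assumed: weekly hazard 0.16 times a site multiplier, within-site hazard ratio 1.9, weekly visits to day 35, 60 per arm, 20,000 trials. Each cell shows pooled / site-stratified log-rank.

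| Site multipliers | Alpha | Power |
|---|---|---|
| None | 5.2 / 5.3% | 81.7 / 81.0% |
| 0.6-1.6 | 4.0 / 4.8% | 77.7 / 80.4% |
| 0.35-2.2 (extreme) | 2.9 / 5.0% | 64.4 / 77.4% |

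**Baseline area, primary outcome.** Assumed: area log-uniform on 5-20 cm², no site effect, odds ratio 2, 3 or 4 per halving of area; 20,000 trials. Chi-square alpha is 5.1, 5.5 and 5.3%. Power is 84.8, 85.2 and 84.5% for chi-square against 86.2, 88.0 and 88.7% for logistic regression on site and log area. The logistic test's own alpha is 5.4-5.8%, so part of that gain is test size.

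**Continuous outcomes.** With baseline correlation ρ, baseline adjustment multiplies the variance by 1−ρ² against a raw post-score and by (1+ρ)/2 against a change score. At the assumed ρ = 0.3, 0.5, 0.7 the equivalent extra sample is 1/(1−ρ²) − 1 = 10, 33, 96% and 2/(1+ρ) − 1 = 54, 33, 18%.

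**The case against.** The strongest reply is that the primary-outcome gain is small and rests on assumption. Under no or mild site effects it lies between −0.4 and +0.3 points, and planned power is reached in every scenario without the change. Large site effects have no support in the documents: all four centres are tertiary hospitals in one state, the dressing is identical, and planimetry is read centrally and blinded. Analysis is by intention to treat with the last measurement carried forward, so 60 per arm is more relevant than 54.

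The Sample Size Calculation also anticipates 85% versus 55% for wound reduction, which is closer to the primary outcome than the 25-point difference in closure. With that 30-point difference, pooled / CMH power at 60 per arm is 96.1 / 95.9, 96.2 / 96.1, 96.6 / 96.9 and 97.3 / 98.1% across the same four site scenarios. At 54 per arm it is 93.9 / 94.0, 93.7 / 94.0, 94.4 / 95.2 and 95.2 / 96.8%. The gain is then at most 1.6 points.

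All of this stands as a limit on size. The largest figures concern secondary outcomes on which the trial was not sized, and the 96% figure applies only to a raw post-score. That case is mainly histology, where the variance formula is only a rough guide for 0-3 scores. The mixed-model and day-0 gaps are missing specification, not power lost through site.

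None of it removes the mismatch between design and analysis. Reapplication at the investigator's judgment and two permitted offloading devices make some site difference plausible, though undocumented. Stratifying costs next to nothing if there is none.

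**Conclusion.** The concern holds as a free improvement, not a validity error. Site-stratified allocation is followed by tests that name neither site nor baseline, and nothing else in the document repairs this.

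For a 25-point difference, the pooled chi-square forgoes about 0-4 power points on the primary outcome in the main scenarios, about 7 under the widest spread tried, and 0 to 1.6 if the difference is 30 points. Its type I error can fall to about 2.5-3% in the extreme 25-85% case, while CMH stays near 5%. For time to closure the loss is about 3 points with moderate site differences and 13 with extreme ones.

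Every gain depends on assumed site effects, baseline correlations or odds ratios, because the documents give none. The point deserves action because the remedy is so cheap, with medium confidence about its size.

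**What to change.** State in the SAP:

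1. **Primary proportion:** CMH test stratified by site, with a Mantel-Haenszel common risk difference and 95% CI. Logistic regression on treatment, site and log baseline area should be supportive only, because its likelihood-ratio test is slightly liberal at this size.
2. **Time to closure:** log-rank test stratified by site, with a supportive Cox model stratified by site and adjusted for log baseline area.
3. **Wound-area mixed model:** list the terms (treatment, visit, treatment-by-visit, site, baseline area).
4. **Day-5 histology:** proportional-odds model for the 0-3 scores with day-0 score and site; ANCOVA with day-0 value and site for capillary density.

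The analysis text is in the past tense, so date the change and say whether outcome data by arm had been seen. If they had, keep the pooled tests as primary and report these as sensitivity analyses.

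The cost is SAP wording and a few lines of code in software the plan already names. Site, baseline wound characteristics and day-0 histology are already recorded. If sites do not differ, the price is about 0.5 power point at most on the primary outcome and 0.7 on time to closure.
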